until thematic saturation is reached.⁵⁸ Interviews will be recorded with permission and transcribed verbatim, and analyzed iteratively (concurrent with ongoing qualitative work) using a general inductive approach.^{59–61} Analysis will be led by Drs. [name] and [name], in partnership with [name] (Co-investigator, Years 1-3), [name] (Years 3-5), [name] (Years 3-5) and [name] (Parent partner). Results summaries will be shared with interview participants, and with hospitals' DALTs, both to return results to participants and to member-check the credibility of findings.^{62,63}

6. Study Population and Setting

Eligibility Criteria. We will limit our analysis to children < 18 years of age admitted with the following common medical reasons for hospitalization: gastroenteritis/dehydration, skin and soft tissue infection, UTI, pneumonia, viral infection not otherwise specified, and influenza. These diagnoses comprise approximately 25% of all unscheduled PHM admissions nationally, and represent conditions that have been identified as appropriate for direct admission but not currently accepted for direct admission at the participating hospitals.^{25,39} Children with planned admissions (i.e. chemotherapy), those admitted to non-PHM Services (i.e. the ICU), and those transferred from other hospitals will be excluded.

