7. Recruitment Plan for Prospective Studies. Each of our three hospital partners examined administrative data from the 2017 calendar year to identify the number of children admitted to their PHM services, with an eligible diagnosis, from our partnering pediatric primary care practices. The resulting projected sample size is shown in Table 5, with hospital-specific estimates provided in Appendix B. Given the availability of historic data from all of our partner sites, we are confident in our sample size estimate. Because our primary outcome will be derived from EHR data, which is available for all hospitalized children by hospital protocol and procedures, we anticipate no missing data for this timeliness outcome. This is also true of our secondary outcomes derived from EHR data, including ICU transfer and rapid response calls. However, for our parent-reported measure of family experience of care, we estimate a response rate of 75%, accounting for potential parental refusals, absence of parents from the bedside, and inability to complete the survey in

Table 5. Estimated Sample Size, Attrition, and Monthly Enrollment

	Estimated number of potentially eligible study participants: Estimated number of children meeting eligibility criteria during two year implementation period, derived from participating hospitals' administrative data (2017).	2288
2.	Total number of study participants expected to be screened: All	2288
3.	Total number of study participants expected to be eligible of those screened: All directly admitted patients, 70% of patients admitted through EDs at children's hospitals, and 95% of children admitted through EDs at our participating community hospital	1696
4.	Target sample size (use same number stated in milestones): Target sample size for direct admission intervention = 190, for ED admission = 1506	1696
5.	If applicable, total number of practices or centers that will enroll participants: 70 primary care and urgent care practices will be randomized	70
6.	Projected month first participant enrolled (month after project initiation):	6 mo
7.	Projected month last participant enrolled (month after project initiation):	45 mo
8.	Projected rate of enrollment: estimated number of enrolled children/mo	70
9.	Estimated percentage of participant dropout: We anticipate a zero drop- out rate for our timeliness primary outcome given its derivation from EHR data.	0%

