English, Spanish, Somali, Nepali or Arabic. (This response rate aligns with past work requesting parental participation in a survey during their hospital stay^{64,65}). To collect this parent-reported outcome, we will approach parents/guardians during their child's hospital stay, either by phone or in-person, keeping with each site's COVID-19 regulations. A research assistant will explain the study, and administer the survey via tablet or via personal cellphone to those parents/guardians who provide informed consent. Our sample size estimate for the relative number of direct admissions is dependent upon three assumptions/components of the direct admission process – first, that approximately 13% of children who are admitted to hospital will be seen by their PCPs prior to hospital admission (an

estimate derived from administrative data at NCH); second that these PCPs will contact the hospital for direct admission (a component of our direct admission intervention education); and third, that the PHM service will deem the child appropriate for direct admission and have a bed available. For this third criteria, we conservatively estimate that 80% of children referred for direct admission from PCPs will be accepted. Based on these assumptions, we estimate that 10% of children cared for by these PCPs will be directly admitted following rollout (Figure 2). Please note that our estimate that 13% of children who are admitted to hospital will be seen by their PCP is conservative; our PCP stakeholder partners have estimated that between 15 and 50% of their admitted patients are seen in their clinics prior to admission. For children considered for direct admission from urgent care centers, we anticipate that eligible urgent care providers will call to request direct admission in 80% of cases, and that 80% of these patients will be accepted. Our projected sample size of children admitted through the ED takes into account our assumption that these children may be more acutely unwell and/or clinically unstable. Correspondingly, we estimate that 70% of children who are admitted through the ED at children's hospitals with our target conditions will be eligible for inclusion, and that 95% of those who are admitted through the ED at our community hospital will be eligible for inclusion (given lower levels of acuity of children admitted to community hospitals).

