9. Outcomes. Our primary outcome, prioritized by multidisciplinary stakeholders including parents and healthcare teams in our preliminary work,³⁹ will be timeliness of clinical care provision. Timeliness of clinical care will be defined as the time from arrival at the hospital until initiation of clinical care by the accepting healthcare provider (including diagnostic testing and/or medical management). This outcome will be derived from EHR time stamps; all project sites use EHRs to document times of patient registration, orders, administration of medications and therapies, and diagnostic tests. EHR time stamps have been previously validated using time motion data;⁶⁸ during the pre-implementation period we will similarly validate the accuracy of time stamps by conducting time motion studies at each hospital.⁶⁹ The feasibility of collecting timeliness outcome data is supported by preliminary data from Lowell General Hospital and PRMC-E, as described above (see Power Calculation, effect size estimation).

Secondary outcomes will include: (i) parent-reported family experience of care (detailed below); (ii) unanticipated transfer to the ICU within 6 hours of hospital admission, a marker of clinical deterioration;³⁸ and (iii) rapid response calls within 6 hours of hospital admission, a second marker of clinical deterioration defined as calls to the hospital's medical-

Table 6. Consumer Quality Index Inpatient
Hospital Care admission module measures
Your rights as patient (complaint procedure,
etc.)
What will happen during this hospitalization
The person in the hospital whom you can
contact if you have questions
What medications you are taking
Any dietary and nutritional requirements
Any hypersensitivity to
substances/medication
Your provisional discharge date
Your personal needs during the
hospitalization
Did the healthcare providers/ staff, upon
arrival to the ward, have enough time for
you?

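### Deterioration in the ED that ends in ICU admission drops out of the safety outcomes, while the same event on the ward after direct admission is counted; this can bias the safety comparison, net direction unknown.

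*Combined protocol and SAP*

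**What the plan says.** Section D.9 (Outcomes) uses two different clocks. The primary outcome is "the time from arrival at the hospital until initiation of clinical care by the accepting healthcare provider". The two deterioration outcomes are "unanticipated transfer to the ICU within 6 hours of hospital admission, a marker of clinical deterioration" and "rapid response calls within 6 hours of hospital admission, a second marker of clinical deterioration". Table 1 times the two deterioration outcomes in the same way.

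Section D.6 (Eligibility Criteria) says that "those admitted to non-PHM Services (i.e. the ICU), and those transferred from other hospitals will be excluded".

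Table 5 expects different shares to be kept by route: "All directly admitted patients, 70% of patients admitted through EDs at" children's hospitals, and 95% at the community hospital. Section D.7 gives the reason for the lower ED share: "these children may be more acutely unwell and/or clinically unstable". For direct admissions it assumes that "80% of children referred for direct admission from PCPs will be accepted". Section D.3 adds a structured tool at the referral call and a stability check by the inpatient team on arrival.

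The plan does not say which time stamp marks hospital admission on each route, or how a direct admission redirected at the arrival check is classified. It does not count deterioration in the ED, and it has no sensitivity analysis that keeps children who go from ED to ICU.

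**The concern.** Take two children with the same illness who both need intensive care two hours after reaching the hospital. The one admitted directly is on the ward and is an event. The one in the ED goes to the ICU, is excluded as a non-PHM admission, and is never counted. Whether an early deterioration is observed thus depends on the route, and the route is what the intervention changes.

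In analysis (i) the two groups have passed different filters before counting starts. In analysis (ii), which keeps the randomized comparison, the exclusion is selection after randomization. The covariates in section D.5 do not correct this: apart from level of care (observation or inpatient), none reflects acute severity at presentation. The supplemental check there compares ED outcomes before and after rollout, but both periods carry the same exclusion, so it cannot reveal the problem.

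Hypothesis 1 predicts no significant difference in deterioration, and these two outcomes are the evidence for it. With opposing selections of unknown size, neither a null result nor a signal could be read with confidence.

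**Working it through.** **1. The plan's denominators.** Figure 2a has 10 post-crossover and 6 pre-crossover cells.
- Direct: 10 × 19 = 190. ED post: 10 × 87 = 870. ED pre: 6 × 106 = 636.
- ED total: 870 + 636 = 1506. All: 1506 + 190 = 1696.

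These match sections D.7 and D.8. The documents give no event rate, margin or power for the safety outcomes.

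**2. Screening by route.** Table 5 goes from 2288 to 1696, a loss of 592. All direct admissions are kept, so the whole loss is on the ED route: 2288 − 190 = 2098 screened, of whom 1506/2098 = 71.8% are kept, against 100% of direct admissions. How many of the 592 are ICU admissions is not stated.

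**3. Effect of the ICU exclusion, analysis (i).** Assume the same true risk q of early deterioration on both routes, and that a fraction f of ED-route deteriorations end in ICU admission from the ED and are excluded. Neither q nor f is in the documents.
- Observed direct risk = q. Observed ED risk = q(1 − f)/(1 − qf).
- At q = 2%, f = 50%: 0.02 × 0.5/0.99 = 1.01%, a ratio of 1.98. That is 3.8 expected events in 190 direct admissions and 8.8 in 870 ED admissions, instead of 17.4.

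| f | apparent ratio R, direct to ED (q = 2%) |
|---|---|
| 10% | 1.11 |
| 25% | 1.33 |
| 50% | 1.98 |
| 75% | 3.94 |

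With q from 1% to 4% the ratios hardly change (3.97 to 3.88 at f = 75%). If ED children are truly 1/(1 − f) times as likely to deteriorate (1.33, 2 or 4 times for f = 25%, 50%, 75%), the bias approximately cancels. Beyond that it reverses.

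**4. Effect of the clock.** This depends on an undefined term.
- *If admission means the ward admission decision*, the ED window starts L hours after arrival. For a hazard that halves every H hours the apparent ratio is 2^(L/H). For L = 2, 4, 6 h it is 1.6, 2.5, 4.0 at H = 3 h, and 1.1, 1.3, 1.4 at H = 12 h. A flat hazard gives 1.0, and a rising one gives less than 1. L and H are assumptions.
- *If admission means ED registration* (section A speaks of admission beginning in the ED), the shift disappears but the exclusion still acts. With a flat, low hazard, and every ED deterioration going to the ICU, the ratio is 6/(6 − L): 1.5 at L = 2 h and 3.0 at L = 4 h.

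**5. Dilution in analysis (ii).** If no pre-crossover child is admitted directly, the apparent post-to-pre ratio is 1 + s(R − 1), where s is the direct-admission share after crossover.
- Figure 2b post-crossover cells, Groups 1 to 4: direct 63 + 34 + 13 + 44 = 154; ED 817 + 497 + 383 + 330 = 2027. So s = 154/2181 = 7.1%.
- Figure 2a: s = 19/106 = 17.9%.

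| f | s = 17.9% (Figure 2a) | s = 7.1% (Figure 2b) |
|---|---|---|
| 25% | 1.06 | 1.02 |
| 50% | 1.18 | 1.07 |
| 75% | 1.53 | 1.21 |

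Figure 2b also shows 6 + 3 + 21 = 30 direct admissions among 608 children in pre-crossover cells (4.9%). Dividing by 1 + 0.049(R − 1) lowers the last column to about 1.01, 1.02 and 1.05. The 27- and 36-month blocks are projections.

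**The case against.** A reader might infer that the design is biased against direct admission, so that equal true risk will appear as excess harm. The documents do not support that. They assume that ED children may be sicker and that one in five PCP referrals will be declined, and they describe a tool for judging suitability before acceptance. These features lower the observed risk on the direct route relative to the ED route. The exclusion also removes ED children who might never have been accepted for direct admission, so keeping all of them in analysis (i) could over-correct. This objection stands, and it limits the claim to a possible bias of unknown sign.

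A reader might also take the clock shift as established. It is not: no time stamp is defined by route, and the ratios in step 4 rest on assumed values.

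The measure can also be defended as a choice of estimand. Stakeholders prioritized the 6-hour outcomes, and the events are routine PHM quality markers. If the question is whether a child was placed correctly on the ward, triage to the ICU from the ED is a real feature of that route. This is a good reason to keep the measures. It does not answer the selection in analysis (ii), which compares practices before and after crossover and not ward placements.

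Finally, these are secondary outcomes, and the distortion in analysis (ii) is small at the current direct-admission share. Both points are correct and limit the importance of the concern.

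**Conclusion.** The asymmetry holds on the text. Early deterioration counts on the ward and disappears when it leads from the ED to the ICU, and nothing in the plan repairs this. Its isolated effect is against direct admission, but the opposing selections leave the net direction unknown.

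Under equal true risk and an assumed 25% to 75% of ED-route deteriorations excluded, the apparent ratio is about 1.3 to 3.9 in analysis (i). In analysis (ii) it is about 1.02 to 1.21 at the Figure 2b share, and less if the pre-crossover direct admissions are allowed for. The structure comes from the documents; q, f, L and H do not. This is worth correcting because the safety hypothesis rests on these outcomes and the repair is cheap. It does not affect the primary outcome.

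**What to change.** 1. In section D.9, keep both 6-hour measures and state which EHR time stamp is time zero for each route.
2. Pre-specify a sensitivity analysis of the ICU outcome at clinic level (analysis ii) that:
   - starts the clock at hospital arrival on both routes, using the time stamp already needed for the primary outcome;
   - uses a window long enough to cover ward time on both routes;
   - keeps target-diagnosis children from study practices who go from ED to ICU;
   - counts ICU care by any path within the window;
   - classifies direct admissions redirected on arrival by intended route.
3. Apply the arrival clock to rapid response calls only if such calls are recorded for children still in the ED. If not, report them as a ward-only measure, since a fixed window from arrival would give ED children fewer ward hours at risk.
4. Report the analysis (i) safety results as subject to both selections: ICU exclusion on the ED route, and screening of direct admissions against a possibly sicker ED group.

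The cost is outcome and analysis wording plus one extra EHR extraction of target-diagnosis ICU admissions from study practices. The downside is added noise, because ICU care by any path includes children already critically ill when they arrive.
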